#### 9.1.2. Adverse Reaction

All noxious and unintended responses to a medicinal product related to any dose should be considered an adverse drug reaction. "Responses" to a medicinal product means that a causal relationship between a medicinal product and an adverse event is at least a reasonable possibility (e.g., the relationship cannot be ruled out).

### **9.1.3. Unexpected Adverse Reaction**

An Unexpected Adverse Reaction is defined as an adverse reaction, the nature or severity of which is not consistent with the applicable product information. For FAB122, the reference safety information is included in the Investigator's Brochure. The reference safety information will be reviewed yearly, and the periodicity of the review will be harmonized with the reporting period of the Development Safety Update Report.

### **9.2. Severity Assessment**

The severity of each AE will be graded by the investigator according to the following criteria:

- Mild: awareness of sign or symptom, but easily tolerated.
- Moderate: discomfort sufficient to cause interference with normal activities.
- Severe: incapacitating, with inability to perform normal activities.

### **9.3. Serious Adverse Event**

A Serious Adverse Event (SAE) is any untoward medical occurrence at any dose that:

- Results in death.
- Is life threatening.
- Requires inpatient hospitalization or prolongation of existing hospitalization.
- Results in persistent or significant disability/incapacity.
- Is a congenital anomaly/birth defect.
- Is a medically important event that may jeopardize the subject or may require medical or surgical intervention to prevent one of the other outcomes listed above.

The term "life threatening" in the definition of "serious" refers to an event in which the subject was at risk of death at the time of the event; it does not refer to an event that hypothetically might have caused death if it were more severe. Death is an outcome of an event. The event that resulted in death should be recorded and reported on the SAE form and documented in the eCRF/study database.

Any hospital admission with at least 1 overnight stay will be considered an inpatient hospitalization. An emergency room or urgent care visit without hospital admission will not be recorded as an SAE under this criterion, nor will hospitalization for a procedure scheduled or planned before signing of informed consent, or elective treatment of a preexisting condition that did not worsen from baseline. However, unexpected complications and/or prolongation of hospitalization that occur during elective surgery should be recorded as adverse events and assessed for seriousness. Admission to the hospital for social or situational reasons (i.e., no place to stay, live too far away to come for hospital visits, respite care) will not be considered inpatient hospitalizations.

#### 9.4. Assessment of Causality

The Investigator must determine the relationship between the administration of Investigational product and the occurrence of an AE/SAE as Unrelated, Unlikely related, Possibly related or Probably related as defined below:

Unrelated or  
Unlikely related: Means a causal relationship of the adverse event to investigational product administration is **unlikely or remote**, or other medications, therapeutic interventions, or underlying conditions provide a sufficient explanation for the observed event.

Event can be readily explained by other factors such as the subject's underlying medical conditions, concomitant therapy, or accident; or there is no temporal relationship between study drug or procedure and the event.

A reasonable possibility or clinical evidence that the study drug or procedure caused the event is lacking.

Possibly or  
Probably related: Means there is a **reasonable possibility** that the administration of investigational product caused the adverse event.

'Reasonable possibility' means there is evidence to suggest a causal relationship between the investigational product and the adverse event.

The AE follows a reasonable temporal sequence from administration of the study drug or procedure and at least one of the following instances of clinical evidence:

- Follows a known or suspected response pattern to the study drug or procedure.
- Is confirmed by improvement upon stopping the study drug, i.e., after single dose (dechallenge).

There is a reasonable possibility that the study drug or procedure caused the event i.e., there is evidence to suggest a causal relationship. In such case, the AE is considered an *adverse reaction* (AR). A *suspected* AR has a lesser degree of certainty about causality than an AR.

Causality should be assessed and provided for every AE/SAE based on currently available information. Causality is to be reassessed and provided as additional information becomes available.

#### 9.5. Reporting Adverse Events

All AEs (regardless of seriousness or relationship to study drug) including those from the time of signing of the ICF through to the follow-up/early withdrawal visit are to be recorded in the subject's source documents and on the corresponding page(s) in the database. Whenever possible, symptoms, signs, and laboratory abnormalities should be grouped as a single syndrome or diagnosis. The investigator should specify the date of onset, severity, action taken with respect to study drug, corrective treatment/therapy given, outcome and

---

his/her opinion as to whether there is a reasonable possibility that the AE was caused by the study drug, according to the definitions noted above. All medications administered to treat an AE must be recorded in the subject's source documentation and documented in the database.

## **9.6. Reporting Serious Adverse Events**

Reporting of SAEs will be conducted in accordance with the appropriate regulatory guidelines. All SAEs that occur from the time of signing the ICF to the follow-up/early withdrawal visit must be reported, whether or not the event is considered associated with the study drug. SAEs must be reported, via eCRF, within 24 hours of site awareness. For Germany, SAEs must be reported immediately (without undue delay) after site awareness, as per German ordinance (§ 12 (4) GCP-V). Safety reporting information and contact numbers will be provided to the clinical site.

The investigator must complete the SAE Reporting Form in English and submit it via eCRF, with other relevant source documentation, to the medical monitor ([contact]) and the Sponsor's Pharmacovigilance (PV) representative within 24 hours of awareness of the event to:

[name] (Head of PV team, Pharmalex)  
[contact] / [contact]  
Email: [contact]

The investigator must also provide with urgent priority (upon receipt of a request) other relevant documentation (e.g., copies of diagnostic test results, hospital discharge summary, and/or autopsy report) and send this information to the Sponsor's medical monitor.

All SAEs and medications administered in association with SAEs must be recorded in the study database. The investigator must also promptly notify the Independent Ethics Committee (IEC) of SAEs, including any follow-up information, in accordance with local institutional policy and applicable regulatory requirements.

The responsible medical monitor at the Sponsor will evaluate causality and expectedness of SAEs and in case of a suspected unexpected serious adverse reaction (SUSAR), such information will be sent to the Sponsor's PV representative for review.

### **9.6.1. Adverse Event Follow-up**

The investigator should take all appropriate measures to ensure the safety of the subjects, including referral to a specialist if indicated. The investigator should follow up on the outcome of any AE until the return to normal or stabilization of the subject's condition.

In case of an SAE, the subject must be followed up until clinical recovery is complete and laboratory results have returned to normal, or until the condition becomes chronic in nature, stabilizes (in the case of persistent impairment), or the patient dies. This implies that follow-up may continue after the subject discontinues from the study and that additional information may be requested.

---

Any SAE brought to the attention of the investigator any time after cessation of study drug and considered by him/her to be caused by the study drug with a reasonable possibility, should be reported through the SAE reporting process.

Within 24 hours of receipt of follow-up information, the Investigator must update the SAE form and submit it by email or fax with other relevant source documentation to the Sponsor's Pharmacovigilance (PV) representative.

### **9.7. Expedited Reporting**

Competent authorities will be notified of any AE associated with the use of the study drug that is both serious and unexpected, in accordance with the appropriate local regulatory guidelines.

The Sponsor's PV representative will report all relevant information about SUSARs that are fatal or life-threatening as soon as possible to the applicable competent authorities in all the countries concerned, and to the Central Ethics Committee concerned (if applicable), in any case no later than 7 days after first knowledge by the Sponsor/designee of such a case, followed by a period of maximum of 8 days to complete the initial preliminary report. All other SUSARs will be reported within a period of maximum 15 days after the Sponsor/designee has first knowledge of the SAE.

The Sponsor/designee will also report any additional expedited safety reports required in accordance with the timelines outlined in country-specific legislation.

The Sponsor/designee will also inform all Investigators as required per local regulation.

Events associated with placebo will usually not satisfy the criteria for a SUSAR and therefore for expedited reporting.

### **9.8. Pregnancy**

According to the recommendations on the CTFG contraception guidance, highly effective contraception measures are required for this study. All females patients who are of reproductive potential will be requested to use (or have their partner use) or practicing adequate birth control methods starting from the time of consent through 30 days after the last dose of study therapy. Longer periods of birth control may be required per local requirements. Acceptable methods of birth control include combined (estrogen and progestogen containing) hormonal contraception associated with inhibition of ovulation (oral, intravaginal, transdermal), progestogen-only hormonal contraception associated with inhibition of ovulation (oral, injectable, implantable), , intrauterine device in place for  $\geq 3$  months, intrauterine hormone-releasing system, bilateral tubal occlusion or vasectomised partner.

If a patient becomes pregnant during the study or within the safety follow-up period defined in the protocol, the Investigator is to stop dosing with study drug(s) immediately.

A pregnancy as such is not an AE, however, it must be reported to the Sponsor within 24 hours of knowledge of the event completing a Pregnancy Reporting Form.

Female patients will be instructed to notify the investigator immediately if they become pregnant during the study. Male patients will be instructed to notify the investigator immediately if their partner becomes pregnant. Pregnant patients will be withdrawn from further study treatment. The patients will also be instructed to report pregnancies discovered after the last visit, if they believe that conception occurred during their participation in the study.

The pregnant patient or partner will be followed until the end of the pregnancy. Any complication during the pregnancy should preferably be reported as an AE. The outcome of the pregnancy must be reported on the Pregnancy Reporting Form. Any spontaneous abortion, stillbirth, birth defect/congenital anomaly, death, or other serious infant condition must be reported and followed up as an SAE. If the pregnancy outcome meets seriousness criteria the both the SAE form and pregnancy form should be forwarded.

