### 5.2. Inclusion Criteria

All patients:

1. who completed the full study period in the main ADORE study (FAB122-CT-2001);
2. whom the investigator has no concern and judges tolerable receiving treatment with FAB122 from a risk and benefit point of view;
3. a female subject should not be able to become pregnant up to 30 days after the last dose of FAB122 and needs to meet at least one of the following criteria:
  - female subject who is not of reproductive potential is eligible without requiring the use of contraception. A woman is considered not having childbearing potential when becoming post-menopausal unless permanently sterile. Permanent sterilisation methods include hysterectomy, bilateral salpingectomy and bilateral oophorectomy. A postmenopausal state is defined as no menses for 12 months without an alternative medical cause.
  - female who is of reproductive potential and has a negative pregnancy test at baseline and is non-lactating. A female subject who is of reproductive potential agrees to use (or have their partner use) adequate birth control methods starting from the time of consent through 30 days after the last dose of study therapy. Longer periods of birth control may be required per local requirements. Acceptable methods of birth control include combined (estrogen and progestogen containing) hormonal contraception associated with inhibition of ovulation (oral, intravaginal, transdermal), progestogen-only hormonal contraception associated with inhibition of ovulation (oral, injectable, implantable), intrauterine device in place for ≥3 months, intrauterine hormone-releasing system, bilateral tubal occlusion or vasectomised partner.
4. a male patient must:
  - agree he will not donate sperm during the period he will be using FAB122 AND use a condom during sexual intercourse with pregnant or non-pregnant women of childbearing potential (WOCBP) partner even if he is vasectomized until 104 days after the last dose.
  - in addition WOCBP partner of the male patient must use the following acceptable methods of birth control during the study and until 104 days after the last dose: combined (estrogen and progestogen containing) hormonal contraception associated with inhibition of ovulation (oral, intravaginal, transdermal), progestogen-only hormonal contraception associated with inhibition of ovulation (oral, injectable, implantable), intrauterine device in

---

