### 11.2. Sample Size Determination

No formal size calculation has been done for the extension study.

The main study plans to include approximately 300 patients. It is anticipated that 200-225 patients might be included in this extension study.

All subjects who completed the full study period in the main ADORE study and providing informed consent to comply with extension trial procedures are eligible to participate in this extension study.

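### The rule for reporting pregnancies after the last visit (Protocol 9.8) is tied to study participation and is narrower than the 30- and 104-day contraception windows in criteria 3 and 4

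*Protocol*

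**What the plan says.** **Contraception windows (Protocol 5.2, also in the Synopsis).** Criterion 3 states that "a female subject should not be able to become pregnant up to 30 days after the last dose of FAB122". Section 9.8 repeats the women's rule: "adequate birth control methods starting from the time of consent through 30 days after the last dose of study therapy". Under criterion 4 the male patient's condom duty applies "even if he is vasectomized until 104 days after the last dose", and his partner must use "birth control during the study and until 104 days after the last dose".

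**Reporting (Protocol 9.8).** Female patients are told to notify a pregnancy that occurs during the study. Male patients are told to notify a partner's pregnancy, with no end date given. Patients are also told to "report pregnancies discovered after the last visit, if they believe that conception occurred during their participation in the study". The site must report any pregnancy to the sponsor within 24 hours of learning of it, and a known pregnancy is followed to its end.

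**Safety follow-up period.** The sentence in 9.8 that tells the investigator to stop dosing applies to a pregnancy during the study or "within the safety follow-up period defined in the protocol". The protocol gives no length for such a period.

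**Sperm donation.** In 5.2 the male patient must "agree he will not donate sperm during the period he will be using FAB122 AND use a condom", and the 104-day limit follows at the end of that sentence. The Synopsis version has an additional 'and' before the 104-day limit.

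**The concern.** The protocol asks patients to avoid conception for a stated time after the last dose, but the instruction on what to report after the last visit uses a different clock, the end of participation. Where participation ends before the contraception window does, a conception can fall inside the window and outside the reporting instruction. A patient who follows the instruction exactly would have no reason to contact the site.

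What is at stake is the completeness of safety information. Long-term safety is the primary objective, and section 9.3 lists congenital anomaly as a criterion for a serious adverse event. Such pregnancies will be few, so each unreported one removes a noticeable share of what could be learned. No efficacy or adverse-event table in the SAP depends on this.

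**Working it through.** The plan gives no figure to reproduce here. The check sets the passages side by side and counts days.

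**Step 1. The two clocks.**

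| Person | Contraception ends (5.2) | Reporting instruction (9.8) |
|---|---|---|
| Female patient | 30 days after last dose | Pregnancy during the study; after the last visit, only if conception is believed to fall within participation |
| Partner of male patient | 104 days after last dose | One sentence with no end date; a second limited, after the last visit, to conception within participation |

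**Step 2. Does other text close the difference?**

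- Table 1 ends with the End of Trial column. Sections 9, 9.5 and 9.6 mention a final follow-up or a follow-up/early withdrawal visit, but none is scheduled after dosing.
- Phone contacts for patients not taking the drug (section 6.4 and Table 1, footnote 5) collect vital status only.
- The undefined safety follow-up period belongs to the stop-dosing sentence. Even if it were defined, it would not set a reporting window.
- The 24-hour rule starts when the site learns of the pregnancy, so it does not help if the patient has not been asked to report it.
- Section 9.6.1 has serious events reported at any time after the drug is stopped, but only those brought to the investigator and judged drug-related. Section 9.8 says that a pregnancy in itself is not an adverse event.

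**Step 3. Size of the gap.** Let W be the contraception window (30 or 104 days, from 5.2) and k the number of days participation continues after the last dose. The documents do not give k, so it is an assumption. Then uncovered days = max(0, W − k).

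- Dosing and participation end together, k = 0: max(0, 30 − 0) = 30 days for female patients; max(0, 104 − 0) = 104 days for partners.
- Patient stops the drug but stays for one further 3-monthly visit (section 6.5 allows this), k = 91 assumed: max(0, 30 − 91) = 0 days for female patients; 104 − 91 = 13 days for partners.
- Same case with the ±1 week visit window of Table 1: k = 98 gives 104 − 98 = 6 days; k = 84 gives 104 − 84 = 20 days. The gap for female patients stays at 0.

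The partner figures apply if the participation-based sentence governs. If the male notification sentence with no end date governs, the partner gap is 0.

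**Step 4. Sperm donation.** Read literally, 5.2 ties the donation ban to the period of drug use and the condom duty to 104 days after the last dose, a difference of 104 − 0 = 104 days. The wording in the Synopsis can be read as applying the 104 days to both duties. The two places therefore do not clearly say the same thing.

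**The case against.** The strongest reply is that section 9.8 is wider than the one sentence suggests. Men are told to notify a partner's pregnancy without a time limit, and the post-visit sentence is worded as an additional instruction, so it need not narrow the male duty. The site's 24-hour duty has no limit on conception date. Section 9.6.1 covers later serious events judged drug-related, which could include a congenital anomaly. The entry criteria also require contraception throughout both windows, so few conceptions are expected.

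Most of this stands, and it rules out several stronger readings that a reader might infer:

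- *That pregnancy follow-up stops when participation stops.* It does not. Section 9.8 follows a known pregnancy to its end. Only the conception window that prompts a report after the last visit is limited.
- *That all partner conceptions in the 104 days go unreported.* The documents support only an internal inconsistency for partners.
- *That the protocol calls the 30 and 104 days periods of drug exposure or risk.* It sets them as contraception durations and gives them no other label.
- *That every remaining patient passed through the full gap because the study stopped early.* SAP sections 2.1 and 6 record early termination, but neither document gives last-dose dates or the interval from last dose to last visit.
- *That a number of affected couples can be stated.* The documents anticipate 200–225 participants but give neither the proportion of men nor the proportion with a partner of childbearing potential.
- *That leaving the male contraception rule out of 9.8 is an error.* Criterion 4 states it in full; repeating it is a matter of preference.

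The reply does not close the gap for female patients, whose two instructions are both tied to the study. Nor does it settle which of the two male sentences applies after the last visit. Consent documents were not available, so what patients are told there cannot be judged.

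**Conclusion.** The point holds as an inconsistency within the protocol. The post-visit reporting instruction in 9.8 is narrower than the contraception windows in criteria 3 and 4, and nothing scheduled in Table 1 makes up the difference. For female patients there is a gap; for partners of male patients the text is contradictory.

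The 30- and 104-day maxima require the last dose and the end of participation to coincide. The smaller figures, 0 days and 13 days (range 6–20), rest on an assumed single further 3-monthly visit. How often either case occurs cannot be determined from the documents, and no number of missed pregnancies is claimed. The undefined safety follow-up period and the sperm-donation wording are separate, smaller drafting faults. None of the three affects the sample size or a planned analysis. The case for acting is that the correction is cheap and improves safety capture in a study whose primary objective is safety.

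**What to change.** 1. Reconcile the Synopsis, section 5.2, Table 1 and section 9.8 so that the conception window prompting a pregnancy report after the last visit is stated relative to the last dose and agrees with the protocol's own contraception windows, for patients and for partners. Make the female and male notification sentences follow the same statement.
2. Give patients that instruction in writing at the last visit.
3. Separately, define the safety follow-up period in the stop-dosing sentence of 9.8 or delete the reference. The reporting window should not be inserted there, because that sentence concerns dosing.
4. Separately, make the end of the sperm-donation clause explicit and reconcile it with the condom clause in both the Synopsis and 5.2. Which duration is right is for the sponsor to settle; this review takes no position.

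The cost is amended wording, matching patient information and one written instruction. It adds no visits or assessments and changes nothing in the SAP.
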